7.9.1.2. Primary Endpoint on Vertebral Body Angles

The primary endpoint on Vertebral Body Angles (VBA) is the mean change of Index Vertebral Body Angles from baseline at 6 months in the subjects treated with Kyphon®Xpede™Bone Cement compared with subjects treated with Mendec Spine Bone Cement. It will be claimed that XPEDE is not inferior to MENDEC with respect to Vertebral Body Angles if the upper bound of the two-sided 95% confidence interval of the difference (Mean Vertebral Body Angles in the XPEDE arm at 6 months - Mean Vertebral Body Angles in the MENDEC arm at 6 months) < 2.5.

X-ray images will be reviewed by independent radiological reviewers who will be blinded to the subjects' treatment groups for each analysis. Adjudications provided both by the site and by the independent reviewers will be analyzed separately. Final conclusion will be made according to independent reviewer adjudication.

The analysis will be performed by means of Generalized Estimating Equation (or mixed models for repeated measures) using patient as the subject. The model will have the Index Vertebral Body Angles as dependent variables and baseline value, number of levels treated (as the multiple data points), type of procedure and arm as explanatory variables. All assumptions for regression models will be assessed by viewing plots of the residual values.

As sensitivity analysis, comparison will be also performed by t-test on:

1. the average value of VBA for the 3 separate treated levels;
2. the value of VBA for all the 3 pooled treated levels.

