Secondary Objective(s)	
Secondary objective is to evaluate the secondary endpoints including:
 
Change of NRS score from baseline at 1 day and 3 months
 
Change of ODI from baseline at 1 day, 3-month visit and 6-month visit.
 
Change of SF-36 from baseline at 1 day, 3-month visit and 6-month visit
 
Change in Vertebral body height restoration at 1 day and 3-month visit and 6 month
 
Change in Vertebral Body Angles from baseline at 1 day, 3-month visit
 
Adverse events through 6-month visit.

Study Design	
This is a single blinded, randomized, multicenter study.
 
Target population are patients who are diagnosed with pathological vertebral body fracture and will undergo BKP or VP procedures.
 
180 patients will be randomized to receive either Kyphon®Xpede™ Bone Cement or Mendec. Timeframe for patient visit includes V1 (pre-operative), V2 (operative), V3 (1d), V4 (3 months), V5 (6 months).

Randomization	180 patients will be randomized into 2 groups in a 1:1 ratio. Permutated block randomization stratified by site, the number of levels to be treated and the type of procedure (VP versus BKP) will be used.
Sample Size	180 patients will be enrolled and randomized
Inclusion/Exclusion Criteria	
Subjects will be included if ALL of the following inclusion criteria are met:
 
1) Subject being diagnosed as having painful pathological vertebral body fracture, who is suitable for VP/BKP procedure (1-3 levels) according to clinic practice.2) Subjects who are willing to participate in study through consent and willing to undergo study specific required procedures with expectancy of geographically stable for follow up duration.3) Subjects are at least 18 and ≤80 years old. 
Subjects will be excluded if ANY of the following exclusion criteria is met:
 
1) Subject has a local or systemic infection2) Subject has pains caused by other spine disease than painful pathological vertebral compression fracture3) Subject has a medical condition with less than 1 year of life expectancy

Medtronic Confidential

This document is electronically controlled

056-F275, v3.0 Clinical Investigation Plan Template

Xpede Clinical Investigation Plan

Version 3 17 Sep 2018

Page 17 of 78

Medtronic

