9.3. Stratification and Treatment Assignment

Randomization will be performed according to a randomization schedule developed by the sponsor or sponsor's representative after the subject has signed the Informed Consent and prior to the surgical procedure. The clinical database will contain the randomization distribution system which will be used for this study.

Individuals who are randomized and receive the study treatment will be considered study (treated) subjects; only data from study (treated) subjects will be included in endpoint analysis.

Patients will be randomized 1:1 to either Xpede™ Bone Cement or Mendec bone cement. The sequence of treatments will be randomly permuted in blocks of 2 or 4 patients per block. The blocked randomization will be centralized and schedules will be created by the study statistician using statistical software. The randomization will be performed by the center via the EDC system (Oracle Clinic). To minimize the selection bias, the randomization procedure for this study will use the site (3 sites), the number of vertebral to be treated (1,2 or 3) and the type of procedure (2 procedure: VP and BKP) as stratification factors, so that there will be a separate permuted block randomization list for each stratum (18). This guarantees treatment balance within strata.

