- 2) Midline height (Hm) is obtained by placing a vertical line along the midline of the vertebral body from the midpoint of the superior vertebral body endplate to the midpoint of the inferior endplate. The height will be measured between the two opposing endplates. If the vertebra is tilted or image obliquely giving a double endplate appearance in the radiograph, the vertical midpoint of the intact endplate lines will be used as the reference point for measurement.
- 3) Anterior height (Ha) is obtained by placing a vertical line along the ventral surface of the vertebral body from the anterior point of the superior vertebral body endplate to the anterior point of the inferior endplate.

[figure not shown]

Figure 3: Vertebral Body Height

[figure not shown]

Figure 4: Examples of Using the Next Adjacent Non-Fractured Vertebra(e)

Magnification Adjustment

Vertebral Body Height will be adjusted for variation in image scale by the use of a magnification marker. The clinical sites are responsible for ensuring the use of magnification markers, provided by Medtronic, on all lateral images. Image readers will measure the diameter of the marker and the

Medtronic Confidential

ratio of the measurement diameter to the true diameter will define the magnification of the image. This magnification will be used to adjust all vertebral body height measurements to a common scale at each visit. If the marker is not present or not measurable at a particular visit, the reviewer may use a stable anatomical feature common with a calibrated visit to make a similar adjustment for scale differences.

B. Vertebral Body Angle

Vertebral body Angle should be assessed at Pre-Operative, 1 days, 3-, 6-month.

- 1) Two lines will be drawn, the first line along the superior endplate of the fractured vertebral body and the second line along the inferior endplate of the fractured vertebral body for each fractured vertebral body.
- 2) The angle between these two lines will then be measured. This is shown in Figure 5. Negative angles will be associated with a kyphosis (wedge-shaped) vertebral body; positive angles will be associated with lordotic (fish-mouthed) vertebral body. A zero-degree angle will indicate that the vertebral endplates are parallel.

[figure not shown]

Figure 5: Example of Measuring Vertebral Body Angle of a Treated Vertebra Vertebral Body Angle of Index Fracture

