The analysis on the second primary endpoint based on Index Vertebral Body Angles will use multiple data points per patient according to the number of levels treated. Assuming not completely independence among measures within same patient the analysis will be performed by means of Generalized Estimating Equation (or mixed models for repeated measures) using patient as the subject. The model will have the Index Vertebral Body Angles as dependent variables and baseline value, number of level treated (as the multiple data points) and arm as explanatory variables. All assumptions for regression models will be assessed by viewing plots of the residual values. It will be claimed that XPEDE is not inferior to MENDEC with respect to Angulation if the upper bound of the two-sided 95% confidence interval of the difference ($\mu_X(t) - \mu_M(t)$) is less than the margin.

The overall study is considered reached if both the null NI hypotheses are rejected. A separate Statistical Analysis Plan (SAP) will be developed prior to data being analyzed to further describe statistical methods, pre-specified data handling rules, and pre-specified analyses that will be included in the final study reports. Any deviation from the pre-specified statistical analyses will be noted in the study report.

The Statistical Analysis Plan will include a comprehensive description of the statistical methods and analyses to be included in reports that include analysis of endpoints. Any change to the data analysis methods described in the CIP will require an amendment only if it changes a principal feature of the CIP. Any other change to the data analysis methods described in the CIP, and the justification for making the change, will be described in the clinical study report.

14. Ethics

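### Strata use the levels planned, but the angle co-primary uses the levels treated, so a planned level left uncemented leaves the comparison and no planned analysis keeps it

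*SAP*

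**What the plan says.** Protocol 9.3 randomises "after the subject has signed the Informed Consent and prior to the surgical procedure" and uses site, "the number of vertebral to be treated (1,2 or 3) and the type of procedure (2 procedure: VP and BKP) as stratification factors". The synopsis agrees: "stratified by site, the number of levels to be treated and the type of procedure (VP versus BKP) will be used". Both strata can therefore only hold planned values.

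The angle analysis is built on a different quantity. Protocol 13.4 says it "will use multiple data points per patient according to the number of levels treated", and lists "baseline value, number of level treated (as the multiple data points) and arm as explanatory variables". SAP 7.9.1.2 adds a procedure term: "baseline value, number of levels treated (as the multiple data points), type of procedure and arm as explanatory variables". Its two t-test sensitivity analyses also rest on treated levels: one uses "the average value of VBA for the 3 separate treated levels", the other pools the treated levels.

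Protocol 9.6 lists the levels treated among the procedure-day data. Protocol 9.8 draws the angle using a line along the superior endplate and "the second line along the inferior endplate of the fractured vertebral body for each fractured vertebral body", so an uncemented fracture can be measured, although the caption of Figure 5 refers to a treated vertebra.

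The neighbouring rules act on patients, not levels. The Full Analysis Set (SAP 7.1.3) needs randomisation and receipt of study treatment. The exit rule (Protocol 9.13) covers a procedure in which no cement was injected. Neither document defines the index levels, or says how an abandoned level, an added level or a switch between vertebroplasty (VP) and balloon kyphoplasty (BKP) is handled.

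**The concern.** Both documents claim the intention-to-treat principle, yet the unit analysed for this co-primary, the level, is selected after assignment. Take a patient randomised in the three-level stratum who is cemented at one level. That patient stays in the analysis set, supplies one angle and, on the plain reading, is modelled as a one-level patient. The two uncorrected fractures do not count.

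The selection could depend on the cement. The trial is single blind, Protocol 9.9 blinds the efficacy assessors and the core laboratory, and nothing describes blinding the operator. Table 2 shows composition differences (benzoyl peroxide 2.5% for Mendec and 0.9% for Xpede). Table 3 has the Xpede working period falling from 30.0 to 11.3 minutes between 15 and 26°C. Cement leakage is a named event. This makes a difference between arms possible; it does not show one.

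At stake is whether the angle comparison is between the groups as randomised. Losing uncorrected levels flatters the arm that loses more of them, and in a non-inferiority test that matters if the arm is Xpede.

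**Working it through.** **The plan's own figure.** Protocol 13.2.2 uses margin 2.5, SD 5.6, true difference 0, one-sided 0.025 and power 0.80.

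- Normal approximation: n per arm = 2 × (1.96 + 0.842)² × 5.6² / 2.5² = 78.8, so 79 per arm or 158 levels. The noncentral t gives 80 per arm or 160 (power 0.801), as stated.
- 160 / 0.80 = 200 levels; 200 / 1.35 = 148 subjects; the next multiple of 18 is 162. All reproduce.

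**Levels exposed.** With the plan's 72/21/7% mix, 180 × 1.35 = 243 levels, or 121.5 per arm. Second and third levels number 180 × (0.21 + 2 × 0.07) = 63, or 31.5 per arm.

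**Abandonment unrelated to arm (precision).** After 20% loss, 243 × 0.80 / 2 = 97.2 levels per arm remain. Design effect = 1 + (2.19/1.35 − 1) × ICC, where 2.19 = 0.72 + 0.21 × 4 + 0.07 × 9. The within-patient correlation (ICC) is an assumption.

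| Levels abandoned | Power, ICC 0 | Power, ICC 0.3 |
|---|---|---|
| 0% | 0.875 | 0.815 |
| 5% | 0.858 | 0.795 |
| 10% | 0.840 | 0.773 |

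**Abandonment that may differ by arm (error rate).** Assumptions:

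- kyphosis scored as positive;
- true six-month means over all planned levels of 3.7 (Xpede) and 1.2 (Mendec), so the difference sits at the 2.5 margin;
- abandoned levels stay at 9.5, close to the 9.523 baseline of the cited cancer-fracture trial (Protocol 13.2.1);
- levels uncorrelated, and SE held at 5.6 × √(2/97.2) = 0.803.

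If a fraction f of second and third levels is abandoned, p = 31.5f / 121.5. The treated-level mean then falls below the planned-level mean by p × (9.5 − 3.7)/(1 − p) in Xpede and p × (9.5 − 1.2)/(1 − p) in Mendec. One-sided error = Φ(−1.96 + net shift / 0.803), where net shift is the Xpede fall minus the Mendec fall.

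| Xpede f | Mendec f | Xpede fall | Mendec fall | Net shift | Error |
|---|---|---|---|---|---|
| 5% | 0 | 0.076 | 0 | 0.076 | 3.11% |
| 10% | 0 | 0.154 | 0 | 0.154 | 3.85% |
| 20% | 0 | 0.317 | 0 | 0.317 | 5.88% |
| 10% | 5% | 0.154 | 0.109 | 0.045 | 2.85% |
| 20% | 10% | 0.317 | 0.221 | 0.096 | 3.29% |
| 10% | 10% | 0.154 | 0.221 | −0.067 | 2.05% |
| 20% | 20% | 0.317 | 0.454 | −0.137 | 1.66% |

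The 5.88% row needs 0.20 × 31.5 = 6.3 abandoned levels in Xpede and none in Mendec. Equal rates are conservative here because 9.5 lies further from the Mendec mean.

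**A second method.** A simulation assumed ICC 0.3, abandoned levels 5 degrees worse and abandonment in Xpede only. It used least squares with patient-clustered errors and no baseline term. With 10% and 20% of multi-level patients' levels dropped, the treated-level estimate fell from 2.5 to 2.31 and 2.12 and the error was 4.4% and 6.3%; the planned-level analysis gave 2.49 and 2.50, with error 2.5%. With nothing dropped the two analyses coincide, yet their separate runs gave 2.6% and 3.7%, so gaps of about one percentage point are within noise.

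**The case against.** Much of the opposing case stands.

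- **Procedure type.** A reader might infer that the model adjusts for the procedure performed while the strata use the procedure planned. The documents do not show this: Protocol 9.3 and SAP 7.9.1.2 both say type of procedure, and if the model takes the stratum value a switch in theatre leaves it unchanged. This is an ambiguity to settle.
- **The covariate.** The parenthesis in "baseline value, number of levels treated (as the multiple data points), type of procedure and arm as explanatory variables" may describe an index of repeated measures within the patient, not a patient-level count. The complaint about adjustment then falls away. The loss of data points does not.
- **Direction.** A reader might infer that the error must favour a non-inferiority claim. Protocol 9.8 scores kyphosis as negative, whereas 13.2.2 says smaller angles are better. Under the 9.8 sign with the stated decision rule, dropping kyphotic Xpede levels raises the Xpede mean and makes the claim harder.
- **Size.** The 3% to 6% range needs abandonment in one arm only. Staying at 9.5 is also doubtful for BKP, since Protocol 4.1 credits balloon inflation itself with angular correction.
- **Occurrence.** The documents describe no abandonment or switch, and Protocol 7.6 says the working period was sufficient under laboratory conditions.
- **Traceability.** Levels treated and extravasation are recorded, and SAP 7.1.2 gives a study treatment deviation as an example of a major deviation. That can expose an imbalance or remove the patient from the per-protocol set; it does not bring back the missing level.
- **Unit.** Treated levels are the unit in which the trial was sized, so redefining the co-primary on planned levels is debatable.

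**Conclusion.** The point holds for levels. Strata are fixed from the levels planned, while the angle co-primary and both its sensitivity analyses take their data points, and apparently a covariate, from the levels treated. No analysis-set or exit rule restores a planned level left uncemented.

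Whether this harms the comparison is conditional. Bias needs abandonment that differs by arm and relates to the angle; otherwise the main cost is precision, at most about four points of power for 10% of levels. No rate is documented, so the error figures are illustrations under the stated assumptions, and their direction waits on the sign convention. No mismatch on procedure type is established, and the stated sample size is sound. This is an inexpensive improvement to the plan; it does not show that the co-primary is invalid.

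**What to change.** 1. In SAP 7.9.1.2 and Protocol 13.4, adjust for the randomisation-stratum value of levels to be treated. State that type of procedure is also the stratum value, as a clarification, and give both documents the same model.
2. Add one eCRF field, completed before surgery, that names the planned levels. The stratum as described holds only a count, and Protocol 9.6 lists only the levels treated, so otherwise the planned levels may not be recoverable.
3. Keep treated levels as the primary data points, and say how levels added in theatre enter.
4. Add one sensitivity analysis of the angle co-primary that includes every planned level, cemented or not, read from the lateral films already taken.
5. Report by arm the planned levels not treated, the levels added and the VP/BKP switches.
6. Reconcile the angle sign between Protocol 9.8 and 13.2.2, so that the direction of any bias can be read.

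The cost is SAP and protocol wording, one eCRF field and a little more core-laboratory reading. The strata are already in the EDC system. The sample size stays at 160 evaluable levels, 200 after loss, 148 subjects rounded to 162, and 180 overall.

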13.3. Data analysis and reporting

The data will be collected from each center in the electronic Case Report Form (eCRF) data base via Oracle Clinic. A specific account number will be given to each center to access the system from any internet-enabled computer. Access to Internet is required for the sites to enter data into the system. User Identification codes will be created to identify data input from each center. The clinical data will be entered by the study staff and transmitted to the central database in an anonymous format so that the study sponsor will not be able to identify the patient, in accordance with the Chinese Data Privacy Directive. Electronic automatic and manual queries will be generated for missing, incorrect or doubtful data and sent directly to the study center via Oracle Clinic.

All the detailed data analyses are described in the Statistical Analysis Plan (SAP). Any change to the data analysis methods described in this section and/or the SAP will require an amendment only if it changes a principal feature of the study description. Any other changes to the data analysis methods will be described and justified in the Final Report or publication.

Based on the clinical practice in the surgery procedures and number of subjects enrolled per center, an investigation of center effect will be investigated including an independent variable for center in the model as well as summary statistics if needed.

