4.2. Secondary Objectives and Endpoints

The secondary endpoints include:

- Change of NRS score from baseline at 1 day and 3-month visit
- Change of ODI from baseline at 1 day, 3-month visit and 6-month visit
- Change of SF-36 from baseline at 1 day, 3-month visit and 6-month visit
- Change of Vertebral body height restoration at 1 day and 3-month visit and 6-month visit
- Change of Vertebral body Angles from baseline at 1 day, 3-month visit and 6-month visit
- Adverse events through 6-month visit. In particular, the following events will be reported:
 - Bone Cement Implantation Syndrome;
 - Bone Cement leakage;
 - Vertebral body compression fracture;
 - Adjacent vertebral body fracture;

5. Investigation Plan

The Xpede Study is a prospective, 1: 1 randomized, single blinded, multi-center human clinical trial designed to confirm the safety and efficacy profile of the Kyphon®Xpede™Bone Cement for regulatory approval in China. This study will enroll up to 180 subjects in order to demonstrate that the Kyphon®Xpede™ Bone Cement is non-inferior to the Mendec Bone Cement by more than a small pre-specified amount in terms of the primary endpoint. This amount is defined as the noninferiority margin (see section 13 from Protocol for details). Subjects will be randomly assigned with a 1:1 ratio to the Kyphon®Xpede™ Bone Cement arm or to the Mendec Bone Cement arm and then followed for a duration of 6 months in all sites. All study sites will be in China. Total duration of the study is anticipated to be approximately 12 months (6 months of enrollments and 6 months follow-up after study procedure).

Patients will be randomized 1:1 to either Xpede™ Bone Cement or Mendec bone cement. The sequence of treatments will be randomly permuted in blocks of 2 or 4 patients per block. The

Xpede Clinical Study

Statistical Analysis Plan

Version 1.0

Page 6 of 19

Medtronic

blocked randomization will be centralized and schedules will be created by the study statistician using statistical software. To minimize the selection bias, the randomization procedure for this study will use the site (3 sites), the number of vertebral to be treated (1,2 or 3) and the type of procedure (2 procedure: VP and BKP) as stratification factors, so that there will be a separate permuted block randomization list for each stratum (18). This guarantees treatment balance within strata.

[figure not shown]

Figure 1: Study Flowchart

6. Determination of Sample Size

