7.3. Center Pooling

The study is a multicenter trial and a multicenter impact on primary outcome will be investigated. A description on primary outcome by sites and a graphical representation of the proportions of safety events for each center will be provided.

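### The SAP's vertebral body angle model omits site, a randomisation stratum, and SAP 7.3 specifies no model for the centre check in Protocol 13.3; the passages need reconciling, and the likely cost is a little precision

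*SAP*

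**What the plan says.** **Stratification.** Protocol 9.3 and SAP section 5 (Investigation Plan) agree. The randomisation will "use the site (3 sites), the number of vertebral to be treated (1,2 or 3) and the type of procedure" as its stratification factors, giving 18 strata with a separate permuted-block list in each.

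**Angle model.** Protocol 13.4 lists "baseline value, number of level treated (as the multiple data points) and arm as explanatory variables". SAP 7.9.1.2 lists "baseline value, number of levels treated (as the multiple data points), type of procedure and arm as explanatory variables". The SAP adds type of procedure. Neither list contains site.

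**Centre effect.** Protocol 13.3 says that "an investigation of center effect will be investigated including an independent variable for center in the model as well as summary statistics if needed". It does not say which model is meant. SAP 7.3 says that "a multicenter impact on primary outcome will be investigated", and the only outputs it names are these: "A description on primary outcome by sites and a graphical representation of the proportions of safety events for each center will be provided".

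**Other relevant places.** SAP 7.9.1 requires both co-primary endpoints to be met. Protocol 6.1 expects three sites, with at least 2 and at most 90 of the 180 patients at any one of them.

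**The concern.** When randomisation balances the arms within site, site differences contribute almost nothing to the error of the arm comparison. A model without site still counts them as residual variance. Its standard error is then too large, its test runs below the nominal 2.5%, and some precision that the stratification paid for is lost. This happens only to the extent that site predicts the outcome beyond the covariates already in the model.

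There is also a question of pre-specification. Protocol 13.3 refers to a centre variable in the model, while the model lists in Protocol 13.4 and SAP 7.9.1.2 have none. With a success-defining endpoint, it should be clear before the data are seen whether the deciding interval is adjusted for site. SAP 7.13 allows departures from the protocol because of data availability, but that cannot be the reason here, since site is known for every randomised patient.

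Finally, a description of outcomes by site need not show the arm difference in each site, which is what a reader would want when one site may supply half the patients.

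**Working it through.** **Inputs from the documents** (Protocol 13.2.2, SAP 6.2): margin 2.5, SD 5.6, true difference 0, one-sided alpha 0.025, power 0.80, 160 levels before loss, 20% loss, 1.35 levels per patient.

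**Assumed input:** R², the share of residual variance due to site after baseline, levels and procedure. The documents give no figure. The range shown is 0 to 0.10.

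**1. The plan's own figure.** The noncentral t calculation at 80 levels per arm gives power 0.801 (79 per arm gives 0.796), so 160 levels is reproduced. 160/0.80 = 200 levels, and 200/1.35 = 148 patients, also as stated. The calculation uses an SD of 5.6 with no gain from covariates.

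**2. Effect of leaving site out, at 80 levels per arm.**
- Standard error reported without site: 5.6 × √(2/80) = 0.885. Half-width: 1.96 × 0.885 = 1.735.
- True standard error under site-balanced allocation: 0.885 × √(1 − R²).
- Excess width: 1/√(1 − R²) − 1.
- True one-sided error without site: 1 − Φ(1.96/√(1 − R²)).
- Power without site: Φ((2.5 − 1.735)/true SE). Power with site: Φ(2.5/true SE − 1.96).

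| Assumed R² | Half-width with site | Excess width without site | One-sided error without site | Power without / with site |
|---|---|---|---|---|
| 0 | 1.735 | 0% | 0.0250 | 0.806 / 0.806 |
| 0.02 | 1.718 | 1.0% | 0.0239 | 0.809 / 0.814 |
| 0.05 | 1.692 | 2.6% | 0.0222 | 0.812 / 0.826 |
| 0.10 | 1.646 | 5.4% | 0.0194 | 0.819 / 0.845 |

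The width and error columns depend only on R². The power column also treats 5.6 as the residual SD.

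**3. Simulation check.** The set-up was 18 strata, blocks of 2 or 4, 152 patients with one outcome each, and 4,000 replicates.
- R² = 0: mean full width 3.589 without site and 3.592 with it; power 0.782 and 0.780.
- R² = 0.05: mean full width 3.593 and 3.505; power 0.784 and 0.798; one-sided error 0.019 and 0.021.

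Power sits near 0.78 because this is 76 outcomes per arm, not 80: 2.5/(5.6 × √(2/76)) − 1.96 = 0.79, and Φ(0.79) is about 0.79. It is not a shortfall caused by omitting site. The simulation covers R² of 0 and 0.05 only, so the other rows are analytic.

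**4. What a by-site comparison could show.** The plan expects 243 levels in 180 patients. After 20% loss and an equal split over three sites, 243 × 0.80/3/2 is about 32 levels per arm per site. The within-site half-width is 1.96 × 5.6 × √(2/32) = 2.7 degrees, wider than the 2.5 margin. At the minimum of 2 patients a site may give no usable estimate.

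Steps 2 and 4 treat levels as independent, as the plan's own calculation does.

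**The case against.** Several stronger readings are tempting, and the documents do not bear them out.

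- **That the SAP removed centre from the protocol's primary model.** It did not. Protocol 13.3 describes an investigation of centre effect, and the protocol's own angle model in 13.4 has no centre term. By adding type of procedure, the SAP model moved closer to the stratification.
- **That the SAP abandoned the centre check.** SAP 7.3 still states that the multicentre impact will be investigated. It names no model, but it rules none out.
- **That the interval will in fact be too wide.** That needs a site effect on the 6-month angle beyond baseline, levels and procedure, and neither document quantifies one. Baseline angle and procedure may absorb part of any case-mix difference. Blinded central reading (Protocol 9.9) and sponsor training of investigators (Protocol 7.6) may reduce other differences. With no site effect there is no widening.
- **That the trial is underpowered or its error rate inflated.** The sample size used an unadjusted SD, and the error moves in the conservative direction.

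It can also be said that the SAP's wording on number of levels may mean the within-patient data points and not the stratum, so it is unclear how many stratification factors the model really carries. A by-site arm comparison would also be too imprecise to settle anything.

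All of this stands, and it limits the point to a small one. It does not explain why a known stratification factor is left out of a success-defining model, or why SAP 7.3 specifies less than Protocol 13.3.

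**Conclusion.** The point holds as a low-cost improvement and a reconciliation of text. Site is a stratification factor missing from the angle model in both documents, and SAP 7.3 does not specify the model-based centre check that Protocol 13.3 describes.

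The statistical cost is conditional and modest. Over an assumed R² of 0 to 0.10, the interval is 0% to 5.4% wider than needed, and adding site gains at most 2.7 points of power (0.819 to 0.845 before rounding) at 80 levels per arm. These sizes rest on the assumed R², on close balance of the arms within site, and on independent levels. The direction favours caution: a false non-inferiority claim becomes less likely, and omitting site does not in itself bring power below 80%.

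**What to change.** 1. In SAP 7.9.1.2, add site as a fixed effect with three levels to the angle model, or state why it is left out. In the same sentence, say whether number of levels enters as the stratification factor.
2. In SAP 7.3, name the model that answers Protocol 13.3: the angle model with an added arm-by-site term, reporting the arm difference and 95% interval for each site. Label it a descriptive consistency check with no decision attached. Say that a site too small for the term to be estimated will be summarised only.
3. Make clear in SAP 7.3 or 7.13 how this relates to Protocol 13.3 and 13.4, so that one interval is identified beforehand as the deciding one.

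The cost is a few lines of SAP text and two degrees of freedom in the primary model. No additional data are needed. With no site effect the loss is negligible: the simulated full width was 3.592 with site against 3.589 without.
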